6.1 DETERMINATION OF SAMPLE SIZE

A total of 70 patients will be randomized in a 1:1 ratio to RO5459072 or placebo (35 patients per treatment group).

Seventy patients (35 per treatment group) will provide power in the range of at least 58 % to 80 % to detect a difference in ESSDAI response rates between treatment groups in the range of 25 % to 33 % (two-sided Chi-square test assuming alpha of 0.05 and placebo rate \leq 25%). This sample size was determined by practical considerations. Seventy patients are also sufficient to provide approximately 70% power to detect a difference of 3 points between treatment arms in change from baseline in ESSDAI score (t-test assuming two-sided alpha 0.05 and standard deviation of 5.0).

Approximately 30 patients will be enrolled into the optional sub-study. It is anticipated that enrollment of a minimum of 30 patients should ensure at least 20 patients (10 per treatment group) complete the study and have biopsy samples taken at both baseline and Week 12, *assuming a maximum drop-out rate of 15%.*

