Continuous secondary endpoints will be analyzed using a Mixed Model for Repeated Measures (MMRM) approach incorporating all observed data up to 12 weeks of treatment. The MMRM will include the absolute change from baseline as the dependent variable. The fixed effects in the model will include treatment, visit (week), treatment-by-visit (weeks) interaction, along with baseline score as continuous covariates. An unstructured variance-covariance structure will be applied to the model.

Additional exploratory analyses will be conducted if deemed appropriate.

PHARMACODYNAMIC ANALYSES

All pharmacodynamic parameters will be presented by listings and descriptive summary statistics separately by treatment group.

PHARMACOKINETIC ANALYSES

The population methods used for modelling of plasma concentration data will be described separately.

SAFETY ANALYSES

Safety data presentations will include all subjects who received at least one dose of the study medication. For these analyses, patients will be grouped according to the treatment actually received.

SAMPLE SIZE JUSTIFICATION

A total of 70 patients will be randomized in a 1:1 ratio to RO5459072 or placebo treatment groups.

A total of 70 patients (35 per treatment group) will provide a power in the range of at least 58 % to 80 % to detect a difference in ESSDAI response rates between treatment groups in the range of 25 % to 33 % (two-sided Chi-square test assuming alpha of 0.05 and placebo response rate \leq 25%). This sample size was determined by practical considerations. Seventy patients also provides approximately 70% power to detect a difference of 3-points between treatment groups in change from baseline in ESSDAI score (t test assuming two-sided alpha of 0.05 and standard deviation of 5.0).

Approximately 30 patients will be enrolled into the optional sub-study. It is anticipated that enrollment of 30 patients should ensure at least 20 patients (10 per treatment group) complete the study and have biopsy samples taken at both baseline and Week 12, assuming a maximum drop-out rate of 15%.

CONCOMITANT MEDICATIONS

In addition to the study drug treatment, patients may continue to concomitantly use existing treatments for Sjögren's syndrome.

Prohibited therapies are:

- Corticosteroid therapy exceeding 7.5 mg prednisone equivalent per day.
- Anti-CD20 therapy (e.g., rituximab) or other B cell-depleting therapy within 6 months of screening.

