3. STUDY DESIGN

3.1 DESCRIPTION OF STUDY

3.1.1 Overview of Study Design

[figure not shown]
Study BP30037 is a randomized, double-blind, placebo-controlled, two-treatment arm, parallel-group study designed to evaluate the effects of RO5459072 treatment on disease activity and symptoms of Sjögren's syndrome in adult patients with moderate to severe primary Sjögren's syndrome. Patients will be randomized 1:1 to receive either 100 mg RO5459072 or placebo orally twice daily (b.i.d.) and will be treated for a maximum of 12 weeks. Based on the Investigator judgment, patients may be re-screened and enrolled if the patient meets all of the eligibility criteria at a later time-point.

Assessments of Sjögren's syndrome disease activity, symptoms and quality of life will be made before (baseline [Week -1]), during the study treatment phase, upon completion and, at the early termination visit and at the safety and follow-up visit in order to evaluate the efficacy of RO5459072 treatment. Patients will start study drug treatment one day after the *last* baseline *assessment*. In addition, patients will undergo pharmacodynamic assessments of exocrine gland function and provide samples for measurement of white blood cell numbers and levels of biomarkers associated with Sjögren's syndrome or connected to the mechanism of action of RO5459072, as well as RO5459072 plasma concentrations. Safety and tolerability will be assessed throughout the study.

At selected participating study centers, patients may also enroll into an optional sub-study in which consenting individuals will undergo minor salivary gland (MSG) biopsies for assessing histological changes in labial salivary glands. Biopsies will be taken at baseline (Week -1) and at the end of the study drug treatment period (Week 12, ± 1 week). The data from the sub-study will be analyzed and reported separately.

Patients may concomitantly receive standard of care symptomatic treatment (see Section [4.5.1](#)).

Figure 3 Study Design

The total duration of the study for each patient will be (up to) 18 weeks:

- Screening visit: Up to 28 days prior to 1st dose.
- Baseline visit (BL): Up to 7 days prior to 1st dose.
- Treatment period: Up to 12 weeks (Days 1 to 84).
- Follow-up visit: 14 days after last dose.

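### Does the stated power need a drop-out allowance for the main study?

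*Combined protocol and SAP*

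**What the plan says.** Section 6.1 randomises 70 patients, 35 per arm, and quotes power for the same 70: "Seventy patients (35 per treatment group) will provide power in the range of at least 58 % to 80 % to detect a difference" in ESSDAI response of 25 to 33 percentage points. The test is a two-sided chi-square at 0.05 with a placebo rate of at most 25%. For the mean change, "Seventy patients are also sufficient to provide approximately 70% power to detect a difference of 3 points between treatment arms", with SD 5.0 and a two-sided t-test. On how 70 was reached: "This sample size was determined by practical considerations". The synopsis repeats both figures ("A total of 70 patients (35 per treatment group) will provide a power in the range of at least 58 % to 80" per cent; "Seventy patients also provides approximately 70% power to detect a difference of 3-points between treatment groups").

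The only drop-out figure in the section belongs to the biopsy sub-study, where 30 enrolled should leave at least 20 with paired biopsies, "assuming a maximum drop-out rate of 15" per cent.

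Other sections settle how dropouts are treated:
- Section 4.7.1: withdrawals are not replaced.
- Section 6.3.1: the modified intent-to-treat (mITT) population needs study drug, a baseline value and at least one post-baseline value.
- Section 6.6.1: a patient without Week 12 data is a non-responder in the primary analysis.
- Section 6.6.2: continuous endpoints use a mixed model for repeated measures (MMRM) on all observed data, with baseline as a covariate.
- Section 3.1.1: disease activity is also assessed "at the early termination visit and at the safety and follow-up visit in order to evaluate the efficacy" of the drug. Appendix 1 schedules the ESSDAI at that early termination visit.

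**The concern.** The number powered equals the number randomised. A reader who sees 15% drop-out allowed for sub-study patients, who are also main-study patients, will ask why the main calculation has none. The non-responder rule sharpens the question. If the 25 to 33 point differences describe patients with Week 12 data, counting dropouts as failures shrinks both response rates and the gap between them. The phrase "Seventy patients (35 per treatment group) will provide power in the range of at least 58 % to 80 % to detect a difference" would then not be a floor over the placebo rates the section allows. The t-test figure would likewise hold only with nearly complete data.

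At stake is how a negative proof-of-concept result is read. At 15% drop-out, on that reading and with placebo at 25%, the chance of missing a true 25-point effect would be about 52% and not 42%. For a 33-point effect it would be about 30% and not 19%.

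**Working it through.** **Inputs.** From Section 6.1: n = 35 per arm, two-sided alpha 0.05, placebo rate p1 at most 0.25, difference 0.25 or 0.33, mean difference 3, SD 5. The main-study drop-out rate q is not in the documents, so it is an assumption here, run from 0 to 15%. The upper value is borrowed from the sub-study sentence.

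**Step 1: reproduce the stated power.** For the chi-square test,

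power = Φ[(Δ√n − 1.96·s0)/s1], with s0 = √(2p̄(1−p̄)) and s1 = √(p1(1−p1) + p2(1−p2)).

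- 25% v 50%: s0 = 0.6847, s1 = 0.6614. (0.25 × 5.916 − 1.96 × 0.6847)/0.6614 = 0.207, so power is 58.2%.
- 25% v 58%: s0 = 0.6968, s1 = 0.6566. (0.33 × 5.916 − 1.96 × 0.6968)/0.6566 = 0.893, so power is 81.4%.
- t-test: noncentrality (3/5) × √(35/2) = 2.510 on 68 degrees of freedom, so power is 69.7%.

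Exact enumeration of the Pearson test gives 59.0% and 80.9%. With 30 per arm the three formula results are 51.6%, 75.0% and 62.8%, which do not match the text. The plan's figures are therefore right for 35 analysed per arm.

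**Step 2: is 58% the minimum over the allowed placebo rates?** With no drop-out, power rises as the placebo rate falls: 61.2% / 83.3% at 20%, 65.5% / 86.1% at 15%, 71.6% / 89.6% at 10%. So 58% is the value at the least favourable rate.

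**Step 3: reading A, rates already count dropouts as failures.** All 35 stay in the denominator and the rates are those of the endpoint as analysed. Power stays at 58.2% / 81.4% whatever q is. With 15% drop-out in both arms, the implied differences among completers are 0.25/0.85 = 0.294 and 0.33/0.85 = 0.388, or about 29 and 39 points.

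**Step 4: reading B, rates apply only to patients with data.** Multiply both rates by (1 − q), keep n = 35, placebo 25%:

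| q | Formula, 25 / 33 points | Exact test | t-test on completers, 35(1 − q) per arm |
|---|---|---|---|
| 0% | 58.2% / 81.4% | 59.0% / 80.9% | 69.7% |
| 5% | 54.7% / 77.8% | 55.9% / 77.8% | 67.4% |
| 10% | 51.3% / 73.9% | 52.6% / 74.6% | 64.9% |
| 15% | 47.9% / 69.8% | 49.1% / 71.0% | 62.4% |

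**Step 5: drop-out at which 58% / 80% is lost under reading B.**

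| Placebo rate | Formula | Exact test |
|---|---|---|
| 25% | 0.3% / 2.0% | 1.6% / 1.4% |
| 20% | 4.7% / 5.0% | 6.3% / 6.7% |
| 15% | 11.6% / 10.1% | 12.1% / 11.3% |
| 10% | 21.4% / 17.5% | 24.8% / 20.6% |

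The thresholds move with the method. The 0.3% entry is about 0.1 of a patient per arm (0.003 × 35), so it has no practical meaning. At a 10% placebo rate the stated figures survive 15% drop-out on either method.

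**Step 6: the continuous endpoint.** The 62.4% is for a completers-only t-test, which is not planned. The MMRM adjusts for baseline and also uses the Week 6 ESSDAI. As an illustration only (the documents give no correlation), a baseline-to-change correlation of 0.40 reduces the residual SD by √(1 − 0.16). With 29.75 per arm the power is then 69.9%, close to the stated figure.

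**The case for a change.** The strongest case for a change is that Section 6.1 never says which reading it intends. A figure worded as a minimum should hold over every placebo rate the section permits. Under reading B with placebo at 25% it fails at almost any drop-out, and at 15% the loss is about 10 points on the formula. The practical origin of the sample size explains 70 patients, but it does not tell a reader what the printed power assumes. One or two sentences would settle it.

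Part of this stands. The silence is real, and the 70% t-test figure is a complete-data figure. Reading A also depends on early leavers having a post-baseline ESSDAI. Before Week 6 that means attending the early termination visit, and those without one fall outside mITT. If every dropout left the analysis at 15%, 29.75 per arm would give 51.3% / 74.6%.

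Reading B itself has no support in the text. The section powers a difference in response rates between the treatment groups, never mentions completers or evaluable patients for the main study, and the endpoint's analysis defines missing as failure. The 15% is stated as a maximum, for a sub-study that needs paired biopsies.

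**Conclusion.** No change is needed. The printed power is arithmetically correct for 35 analysed per arm. It also agrees with the non-responder rule in Section 6.6.1 if the response rates count dropouts as failures and essentially all 35 per arm enter mITT. That is the ordinary reading of a response rate for this endpoint.

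The larger loss, to about 48% / 70% (exact 49% / 71%), rests on three assumptions that the plan does not make: rates among patients with data, placebo at exactly 25%, and 15% drop-out in both arms. The fall from 70% to 62% for the mean difference applies to a test that will not be run, and the MMRM may recover some or all of it.

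The plan already shows that power is modest, as low as 58%, and that practical limits set the size, which is a fair trade-off in a Phase 2a study. Stating the drop-out assumption would be a courtesy to readers. It would alter no patient number, analysis or conclusion. Analysts reading Sections 6.1 and 6.6.1 together can fill the gap sensibly.

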6.2 SUMMARIES OF CONDUCT OF STUDY

Protocol deviations will be listed. The number of *patients* who were randomized, discontinued or completed the study will be summarized by treatment groups.

6.3 ANALYSIS POPULATIONS

6.3.1 Efficacy Analysis Population

All efficacy outcomes will be analyzed according to the mITT principle. The mITT population will comprise of all patients who are randomized, received study drug and have evaluable measurement of the parameter of interest at baseline and at least one post-baseline visit. For all efficacy analyses, the treatment groups will be based on the treatment assigned at randomization.

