Patients consenting to also participate in the optional sub-study will undergo minor salivary gland (MSG) biopsies at baseline and Week 12. Biopsy samples will be processed for histological examination.

The outcomes for the optional sub-study are as follows:

- Change from baseline in focus score (number of lymphocytes per 4 mm²).
- Change from baseline in numbers of defined sub-populations of infiltrating lymphocytes.
- Subjective evaluation of changes from baseline in minor salivary gland (MSG) structure.

Other exploratory analyses may include, but not be limited to, changes in leukocyte and stromal subpopulation numbers and degree of activation.

INVESTIGATIONAL MEDICINAL PRODUCT(S)

The investigational medicinal products in this study are:

- RO5459072 50 mg capsules for oral administration (Formulation F03)
- Placebo capsules for oral administration (Formulation F04).

All IMPs will be supplied and packaged by the Sponsor.

Study drugs are to be taken orally twice daily (b.i.d.) with food, i.e., with breakfast in the morning and a meal in the evening, for 12 weeks. Capsules should be swallowed whole.

Patients will be randomly assigned to one of two possible blinded study drug treatments:

- 100 mg RO5459072 (2 x F03 capsules) b.i.d. with food for 12 weeks (Weeks 1 to 12).
 - Placebo (2 x F04 capsules) b.i.d. with food for 12 weeks (Weeks 1 to 12).
-

PROCEDURES

A Schedule of Assessments (SoA) is provided (see Appendix 1).

STATISTICAL METHODS

EFFICACY ANALYSES

Efficacy analyses will include modified intent-to-treat (mITT) population which is defined as all randomized *patients* who received at least one dose of double-blind study medication and have evaluable measurement of the parameter of interest at baseline and at least at one post-baseline visit.

The proportion of *patients* who have ≥ 3 -point reduction from baseline in ESSDAI score after 12 weeks of treatment will be compared between the two treatment arms using a Pearson Chi-square test (*two-sided p-values, alpha 0.05*). *The difference in proportions and corresponding 95% CI will be provided. Supportive analyses will be conducted if deemed necessary. Patients with missing data at Week 12 will be treated as non-responders in the analysis. Other methods of imputation for missing data will be described in the protocol and statistical analyses plan.*

Secondary endpoints that are binary will be analyzed using similar methods used for analyzing the primary endpoint.

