6. STATISTICAL CONSIDERATIONS AND ANALYSIS PLAN

The database will be cleaned and frozen when all patients have completed the study or discontinued. The treatment assignment will then be unblinded and analyses will be performed on all data.

All efficacy outcomes will be analyzed using modified intent-to-treat population (mITT) which is defined as all randomized subjects who received any study medication and have evaluable measurement of the parameter of interest at baseline and at least one post-baseline visit. For all efficacy analyses, the treatment groups will be based on the treatment assigned at randomization.

All safety analyses will include all randomized patients who have received any study drug. For these analyses, patients will be grouped according to the treatment actually received.

There will be no adjustment made for any multiple comparisons. To aid the interpretation from the formal hypothesis testing, two-sided 95% confidence intervals will be provided.

Descriptive summaries will include mean, standard deviation, median and range for continuous variables and counts and percentages for categorical variables.

Details of statistical analyses will be provided in the statistical analysis plan.

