6.6 EFFICACY ANALYSES

6.6.1 Primary Efficacy Endpoint

The primary endpoint is the proportion of patients who have ≥ 3 point reduction from baseline in ESSDAI score after 12 weeks of treatment. The proportion of *patients* who have ≥ 3 point reduction from baseline in ESSDAI score after 12 weeks of treatment will be compared between the two treatment arms using a Pearson Chi-square test (*two sided p-values, alpha 0.05*). The difference in proportions and corresponding 95% confidence interval (CI) will be provided. *Patients with missing data at Week 12 will be treated as non-responders in the analysis.*

Sensitivity analyses will be conducted if deemed necessary, including sensitivity analyses for handling missing data (e.g., *completer's analysis* or *last observation carried forward (LOCF) method* for missing observations).

In addition; the proportion of patient who have ≥ 3 point reduction from baseline in ESSDAI score after 12 weeks of treatment will be analyzed using a logistic regression model, adjusting for baseline ESSDAI score.

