6.6.2 Secondary Efficacy Endpoints

Secondary endpoints that are binary will be analyzed using similar methods used for analyzing the primary endpoint.

Continuous secondary endpoints will be analyzed using a Mixed Model for Repeated Measures (MMRM) approach incorporating all observed data up to 12 weeks of treatment. The MMRM will include the absolute change from baseline as the dependent variable. The fixed effects in the model will include treatment, visit (week), treatment-by-visit (weeks) interaction, along with baseline score as continuous covariates. An unstructured variance-covariance structure will be applied to model the within-patient errors, and the restricted maximum likelihood method will be used for estimating the variance components. The denominator degrees of freedom will be estimated using *the Kenward-Roger approximation*.

The least squares mean of change from baseline for each treatment group together with a 95% CI will be calculated from the MMRM model for each visit. At Week 12, the placebo-corrected difference will be estimated from the same MMRM model and will be used to test the null hypothesis of zero difference.

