Appendix 1 Schedule of Assessments (cont.)

1	First study drug administration should be one day after the last baseline assessment.
2	Physical examination includes weight, heart and respiratory rate, and body temperature.
3	All women will have serum pregnancy tests performed at screening and baseline. A urine pregnancy test will also be done at baseline prior to randomization. All women of childbearing potential will have serum and urine pregnancy tests at each subsequent visit.
4	The same salivary or tear sample is used for volume and biomarker assessments (see Section 4.6.1.3.4.).
5	Only markers required for ESSDAI scoring will be collected.
6	Safety laboratory assessment consists of hematology, blood chemistry, coagulation, lipids and urinalysis.
7	MSG biopsies procedures for the optional substudy may be performed at separate study center visits providing the procedures are carried out within the windows specified for the main study.
8	Screening, baseline and on-treatment visit schedules are all relative to the first day of study drug administration (Day 1). The follow-up visit is scheduled relative to the Week 12 end-of-treatment visit (+14 days after the end-of-treatment visit [\pm 7 days]).

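### The mITT rule removes dosed patients with no post-baseline ESSDAI before the non-responder rule can count them, which can shift the response difference in either direction

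*Combined protocol and SAP*

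**What the plan says.** The analysis set is defined in three places with the same content. Section 6.3.1 requires randomisation, receipt of study drug, and that patients "have evaluable measurement of the parameter of interest at baseline and at least one post-baseline visit". The opening of Section 6 applies this to all efficacy outcomes, for randomised subjects who "received any study medication and have evaluable measurement of the parameter of interest at baseline and at least one post-baseline visit". The synopsis, under efficacy analyses, says they must "have evaluable measurement of the parameter of interest at baseline and at least at one post-baseline visit".

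The missing-data rule for the primary endpoint is in Section 6.6.1: "Patients with missing data at Week 12 will be treated as non-responders in the analysis". The same section adds "Sensitivity analyses will be conducted if deemed necessary", with completers and LOCF as examples. Section 6.6.2 carries the approach to the ESSPRI responder endpoint: "Secondary endpoints that are binary will be analyzed using similar methods used for analyzing the primary endpoint".

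In the Appendix 1 schedule, ESSDAI is scored after baseline at Week 6, Week 12, Follow-up and Early Termination, and not at Week 2 or Week 9. Section 3.1.1 confirms that activity is also assessed "at the early termination visit and at the safety and follow-up visit in order to evaluate the efficacy". A footnote to the autoantibody row for those last two visits ("Only markers required for ESSDAI scoring will be collected") shows that scoring there is intended. Section 4.7.1 ends all follow-up once consent is withdrawn and does not replace patients who withdraw. Section 6.2 summarises discontinuations by arm.

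**The concern.** The two rules act in sequence, and the first defeats the second for one group. The non-responder rule is meant to make early loss count against treatment. The mITT filter removes the earliest losses before that rule applies.

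The group is narrow. An early dropout who has an ESSDAI at Early Termination or Follow-up stays in the set and counts as a non-responder. The patient who disappears has a baseline score, takes at least one dose, leaves before the Week 6 assessment and provides neither of those later scores, for example after withdrawing consent.

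If these losses differ between arms, the comparison is no longer between the groups as randomised and dosed. With 35 per arm, one or two patients can move a borderline p-value across 0.05. Neither named sensitivity analysis helps, because completers and LOCF both need a post-baseline value. The baseline-adjusted logistic regression falls under the same population rule.

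**Working it through.** **Inputs from the plan.** 35 per arm, two-sided alpha 0.05, placebo response at most 25%, difference 25 to 33 points (Section 6.1); Pearson chi-square (Section 6.6.1), taken without continuity correction.

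**Assumed inputs.** The number of dosed patients with no post-baseline ESSDAI, and the responder counts. The plan gives no drop-out rate for the main study; its 15% maximum belongs to the biopsy sub-study.

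**The plan's own figure.** Power = Φ{[Δ√n − 1.96√(2p̄(1−p̄))] / √(p₁(1−p₁) + p₂(1−p₂))}.
- 25% vs 50%: (0.25 × 5.916 − 1.96 × 0.685) / 0.661 = 0.207, so power is 58.2%.
- 25% vs 58%: (0.33 × 5.916 − 1.96 × 0.697) / 0.657 = 0.893, so power is 81.4%.

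Exact enumeration gives 58.9% and 80.8%. The stated 58% to 80% is reproduced. It assumes that all 35 per arm are analysed.

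**Effect of deletion.** With x responders among n dosed patients, of whom k have no post-baseline ESSDAI, the non-responder rule gives x/n and the mITT rule gives x/(n−k). The rate in that arm rises. Losses on drug widen a positive difference, losses on placebo shrink it, and equal losses multiply it by n/(n−k).

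**Illustration, 15 responders on drug and 8 on placebo.** The test is z = (p₁ − p₂) / √[p̄(1−p̄)(1/n₁ + 1/n₂)].
- All dosed: 0.2000 / √(0.3286 × 0.6714 × 2/35) = 1.781, p=0.075.
- Two deleted on drug: 0.2260 / √(0.3382 × 0.6618 × 0.05887) = 1.968, p=0.049.

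| Deleted (drug, placebo) | Rates compared | Difference (points) | p |
|---|---|---|---|
| 0, 0 | 15/35 vs 8/35 | 20.0 | 0.075 |
| 1, 0 | 15/34 vs 8/35 | 21.3 | 0.061 |
| 1, 1 | 15/34 vs 8/34 | 20.6 | 0.073 |
| 2, 1 | 15/33 vs 8/34 | 21.9 | 0.059 |
| 2, 0 | 15/33 vs 8/35 | 22.6 | 0.049 |
| 3, 1 | 15/32 vs 8/34 | 23.3 | 0.047 |
| 5, 1 (extreme) | 15/30 vs 8/34 | 26.5 | 0.028 |
| 0, 2 | 15/35 vs 8/33 | 18.6 | 0.105 |
| 1, 5 (extreme) | 15/34 vs 8/30 | 17.5 | 0.147 |

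A result can also be lost: 17/35 vs 9/35 is 22.9 points, p=0.048; one placebo deletion (9/34) makes it 22.1 points, p=0.058.

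**Rejection rate under no effect.** Exact binomial enumeration, 35 per arm, response 25% in both arms when all dosed patients are counted, every excluded patient a non-responder:

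| Excluded (one arm, other arm) | Two-sided rejection rate |
|---|---|
| 0%, 0% | 4.8% |
| 5%, 5% | 5.2% |
| 5%, 0% | 5.4% |
| 15%, 3% (extreme) | 6.5% |

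**Power cost of counting everyone.** 50% vs 25% among patients who stay, equal exclusion in both arms: 55.9% (all dosed) vs 57.1% (mITT) at 5% excluded; 52.6% vs 54.8% at 10%; 58.9% for both with none.

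**The case against.** The strongest reply is about size. To be affected, a patient must miss Week 6 (window from Day 35), Week 12, Early Termination and Follow-up. Section 4.7.1 separates stopping drug from leaving the study, so a patient who only stops drug can still be scored. What remains is mainly consent withdrawal or loss to follow-up in the first five weeks, and nothing in the documents predicts an imbalance. This stands, and it limits the likely effect.

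The error-rate figures also need care. Excluding 5% equally from both arms already gives 5.2%, so most of the rise from 4.8% to 5.4% comes from changed denominators in a discrete test. The 6.5% needs 15% of one arm to have no post-baseline ESSDAI, which is extreme. Both points stand.

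Bias also depends on the null chosen. If response is 25% in both arms among patients who stay, and 15% vs 3% are excluded, mITT rejects 5.1% of the time and the all-dosed analysis 5.7%. That is correct. But Section 6.6.1 has already chosen to treat missing Week 12 data as failure, and under that choice the all-dosed null is the relevant one.

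The ESSPRI gap is smaller, because ESSPRI is also collected at Weeks 2 and 9. Finally, Section 6 defers detail to a statistical analysis plan, and the sensitivity analyses are given only as examples. No separate plan is in the text reviewed, so one might add an all-dosed analysis; to make it primary, it would have to depart from the protocol's stated population.

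**Conclusion.** The concern holds. As written, the non-responder rule does not reach a dosed patient who has a baseline ESSDAI and none afterwards, and no named analysis brings that patient back. The bias can run in either direction. In the assumed example, two one-sided exclusions move a 20.0-point difference to 22.6 or 18.6 points, and p from 0.075 to 0.049 or 0.105. One exclusion, or one in each arm, does not cross 0.05 from that starting point.

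All counts are assumptions. The reading also takes an Early Termination or Follow-up score to be a post-baseline visit; if it were not, more patients would be excluded. The stated power is not in error. The issue is modest in expected size, but worth settling before unblinding because it concerns the primary set and is cheap to close.

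**What to change.** For the primary endpoint and the binary ESSPRI endpoint, define the analysis set as all randomised patients who received at least one dose and have a baseline value of the parameter, analysed as randomised, with any patient lacking a Week 12 value counted as a non-responder. Keep the present mITT set for the MMRM analyses and as a sensitivity analysis of the two binary endpoints.

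The change touches the synopsis, the opening of Section 6, Section 6.3.1 and the statistical analysis plan. It needs no new data. Observed response rates may be slightly lower if such dropouts occur. The power cost under equal exclusion is 57.1 − 55.9 = 1.2 points at 5% and 54.8 − 52.6 = 2.2 points at 10%.
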